4.0 STUDY CALENDAR

4.1 Test Schedule

Tests and procedures ¹				Active Treatment				End of Treatment	
	≤28 days prior to registration	≤14 days prior to registration	≤7 days prior to registration	Cycle 1			Prior to Day 1 of subsequent cycles ³	Every 2 months	
				D1	D3	D10 ²			
Tests and procedures ¹	Window:						±3 days	±7 days	±14 days
Clinical Procedures									
Vital signs, history (including personal/family history for prolonged QTc) and exam, weight, PS		X		X	X	X	X		X
Height		X							
Review of concurrent medications ⁴		X					X		
Pregnancy test ⁵			X						
Blood pressure monitoring ⁶		X		X	X	X	X		
Adverse event assessment		X		X	X	X	X		X
Consultation with endocrinologist, cardiologist, or nephrologist for blood pressure management		X					X		
Hematology: CBC/diff ⁷		X					X		X
Chemistry Panel ⁸		X					X		X
TSH		X					X		
24 hr urine catecholamine and metanephhrines		X					X		
Plasma fractionated metanephhrines		X					X		
Urinalysis ⁹		X					X		
Urine protein/creatinine ratio		X					X		
Genetic counseling and testing at discretion of patient and counselor ¹⁰	X								

¹ All tests and procedures are clinically indicated, unless noted with an R to indicate funding by research

² May be omitted at discretion of treating provider and replaced with telephone call contact.

³ If patient is tolerating treatment well, return visits may be performed over the phone for non-imaging cycles (starting with cycle 3, 5, 7 etc.). During these phone visits the patient status, treatment information, and Adverse Event Assessments must be assessed and recorded. Labs may be done locally and transmitted to Mayo Clinic.

⁴ Concurrent/concomitant medications are reviewed every cycle. Only requested medications are recorded in the study case report forms.

⁵ For women of childbearing potential only. Must be done ≤7 days prior to registration

⁶ Note: 1) daily monitoring of blood pressure is REQUIRED and must be recorded in patient diaries throughout the entire duration of therapy; 2) any systolic BP >150 mm Hg and/or diastolic BP >100 mm Hg must be brought to the attention of treating provider <24h after noted; 3) any systolic BP >200 mm Hg and/or diastolic BP >110 mm HG should prompt immediate cessation of lenvatinib therapy maintained until remediation to <150 mm Hg systolic is accomplished.

⁷ Must include: hemoglobin (hgb), MCV, leukocyte count, neutrophils (ANC), monocyte count, lymphocyte count, and platelet count (PLT)

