9.72 Hypertension

Hypertension is an important AE associated with lenvatinib (Schlumberger, Tahara et al. 2015). Frequent blood pressure (BP) monitoring is important in subjects receiving lenvatinib. In addition patients with secretory pheochromocytomas and paragangliomas are at risk for hypertension and hypertensive crisis by virtue of disease. Patients will be provided with a diary in which to record their daily BP readings (see [Appendix VI](#)) for first three cycles. Daily readings should be taken. If the systolic reading is >140 mmHg OR the diastolic reading is >90 mmHg OR any combination of elevated systolic and diastolic readings, patients will be instructed to retake their blood pressure within 1-4 hours. If a second consecutive reading is elevated patient will be instructed to contact their physician as soon as possible. Patients should seek medical advice if their BP exceeds 180 mmHg (systolic) or 105 mmHg (diastolic) at any time and should also be encouraged to contact their physician if they are concerned about any symptoms that may be associated with high BP (e.g., headache). In addition, expert consultation and follow-up for patients with secretory tumors will be required prior to enrollment, and during the study. Experience to date suggests that increases in BP may occur following dosing with lenvatinib for a number of weeks and that these increases may occur relatively quickly. It is imperative that the investigator institute appropriate measures to control BP. This may necessitate changes to existing antihypertensive medication, addition of new medication(s) and/or holding therapy with lenvatinib. Considering the potential of this adverse event we will monitor patients closely in the initial weeks with frequent measurement of blood pressure in clinic on Day 1, 3 and 10.

Recommendations for hypertension monitoring and management are presented in [Appendix IV](#).

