Appendix IV Hypertension Management Guidelines

D.1. Guidelines for the management of lenvatinib-Induced Hypertension: Non-secretory tumors

(For secretory tumors please see Section D.2.)

Increases in blood pressure (BP) and cases of hypertension have been associated with many drugs acting on the VEGF pathway. The proposed mechanism for this increase is through inhibition of VEGF-induced peripheral vasodilation. Hypertension following lenvatinib is well documented in clinical trials. With secretory paraganglioma and pheochromocytoma this could be a major toxicity.

NOTE: that hypertension management of secretory tumors is more complex due to the additional risk of hypertension issues in these patients and management is discussed separately below. For example consultation with HTN specialist is required in patients with secretory tumors prior to study initiation.

- While subjects are receiving treatment with lenvatinib, the early initiation of antihypertensive treatment for grade 1 or 2 hypertension to minimize more severe or persistent hypertension is not considered a grade 3 AE.
- Decisions to hold or decrease the lenvatinib dose during treatment must be based on BP readings taken in the clinic by a medical professional.

Recommended Hypertension Monitoring and Management for non-secretory tumors (BP in mmHg)

Grade (CTCAE v4)	Antihypertensive Therapy	Blood Pressure Monitoring	Lenvatinib Dose Modification
Persistent* Grade 1 Pre-hypertension Systolic 120-139 Diastolic 80-90		Standard	No Change
Persistent Grade 2- Moderate Systolic 140-159 Diastolic 90-99 Protocol-specific guidance supersedes any other management guidelines, including CTCAE v4.	Step 1) Initiate anti-hypertensive treatment (calcium channel blocking agents, e.g. amlodipine, are generally the preferred agents) and if needed, after 24-48 hr Rx, increase dose in stepwise fashion every 24-48 hours until BP is controlled or at max dose of Rx Step 2) If BP still not controlled, add another anti-hypertensive Rx, a LA DHP CCB, ACE1, ARB, or ABB; increase dose of this drug as described in Step 1 Step 3) If BP still not controlled, add 3 rd drug from the list of anti-	BP should be monitored as recommended by the treating physician	No change except as described in Step 4

Recommended Hypertension Monitoring and Management for non-secretory tumors (BP in mmHg)

Grade (CTCAE v4)	Antihypertensive Therapy	Blood Pressure Monitoring	Lenvatinib Dose Modification

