	
hypertensives in Step 2; increase dose of this drug as described in Step 1
 
Step 4) If BP still not controlled, discontinue lenvatinib until BP controlled, then resume
 
NOTE: Stopping or reducing the dose of lenvatinib is expected to cause a decrease in BP.
 
The treating physician should monitor the subject for hypotension and adjust the number and dose of anti-hypertensive medication(s) accordingly
		
Persistent Grade 3 Severe Systolic ≥ 160 Diastolic ≥ 100 Protocol-specific guidance supersedes any other management guidelines, including CTCAE v4	
HOLD lenvatinib until systolic BP ≤ 159 and diastolic BP ≤ 99
 
BP management is identical to that for Grade 2 (see Steps 1-4 above) with 2 major exceptions:
 
1) If systolic BP > 180 or diastolic BP > 110 and the subject is symptomatic: optimal management with intensive IV support in ICU; STOP lenvatinib and notify hospital staff that stopping drug may result in a decrease in BP and
 
2) If systolic BP > 180 or diastolic BP > 110 and the subject is asymptomatic, consideration to initiation of 2 new antihypertensives together should be given in step 1 (and dose escalated appropriately as in step 1).
	
BP should be monitored as recommended by the treating physician unless the subject is symptomatic with systolic BP > 180 or diastolic BP > 110 in which case, monitoring should be intensive
	
HOLD lenvatinib until systolic BP ≤ 159 and diastolic BP ≤ 99. After this, lenvatinib may be re-administered. If BP is still Grade 2, manage as described above for Grade 2 hypertension.
 
In most circumstances, if BP cannot be controlled after an optimal trial of antihypertensive medications, consider either 1 dose reduction of lenvatinib when systolic BP ≤ 159 and diastolic BP ≤ 99 or stopping lenvatinib.
 
HOWEVER, If the subject requires hospitalization for management of symptomatic systolic BP > 180 or diastolic BP > 110,

Recommended Hypertension Monitoring and Management for non-secretory tumors (BP in mmHg)

Grade (CTCAE v4)	Antihypertensive Therapy	Blood Pressure Monitoring	Lenvatinib Dose Modification

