Appendix VI Patient Blood Pressure Diary

Today's date _____

Patient Initials _____

Patient Study ID _____

INSTRUCTIONS TO THE PATIENT:

1. Your blood pressure readings have two numbers. The first number is the pressure in your blood vessels during a heartbeat (systolic), and the second number is the pressure in the vessels when the heart rests in between beats (diastolic). These numbers are usually written with a slash in between them (for example, 110/85).
2. Record the date, then record your blood pressure once daily:
3. If you take your blood pressure at other times of the day, please record the numbers and time under "Other readings".
4. Normal blood pressure is usually considered to be 120/80 mmHg. If your systolic pressure is greater than 140 or your diastolic blood pressure is greater than 90 when you measure your blood pressure. Repeat your blood pressure within 1-4 hours. If your blood pressure is still elevated please contact your doctor's office at [REDACTED] for instructions. Also, you should contact your doctor's office at any time your blood pressure exceeds 180 mmHg (systolic) or 105 mmHg (diastolic), or at any time you have symptoms that you think may be related to hi blood pressure (examples include headache, nausea, vomiting, confusion, anxiety, restlessness). If you need to call after business hours or during holidays or weekends, please call [REDACTED] and ask for the Medical Oncologist on call.
5. Please bring this form to your visit at the end of Cycle 1, 2 and 3.

Date	Blood Pressure readings	Other readings (include time of day)	Date	Blood Pressure readings	Other readings (include time of day)
	/			/	
	/			/	
	/			/	
	/			/	
	/			/	
	/			/	
	/			/	

Date	Blood Pressure readings	Other readings (include time of day)	Date	Blood Pressure readings	Other readings (include time of day)
	/			/	
	/			/	
	/			/	
	/			/	
	/			/	
	/			/	
	/			/	
	/			/	
	/			/	
	/			/	
	/			/	
	/			/	
	/			/	
	/			/	
	/			/	
	/			/	
	/			/	
	/			/	
Patient's Signature: _____					
Date: _____					
Physician's Office will complete this section:					
Date of this clinic visit		Physician/Nurse/Coordinator's Signature			

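### After an extreme blood pressure reading, footnote 6 of the Test Schedule sets no diastolic restart limit, and its systolic limit differs from Appendix IV

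*Combined protocol and SAP*

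**What the plan says.** **Footnote 6, Section 4.1 (all patients).** Item 1: "daily monitoring of blood pressure is REQUIRED and must be recorded in patient diaries throughout the entire duration of therapy". Item 2: readings above 150 systolic and/or 100 diastolic "must be brought to the attention of treating provider <24h after noted". Item 3: "any systolic BP >200 mm Hg and/or diastolic BP >110 mm HG should prompt immediate cessation of lenvatinib therapy", and that stop is "maintained until remediation to <150 mm Hg systolic is accomplished". Item 3 does not say whether the reading is taken at home or in clinic, and its restart condition has no diastolic part.

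**Appendix IV, D.1 (non-secretory) and D2 (secretory).** For Grade 3 hypertension (≥160 systolic, ≥100 diastolic), both tables hold drug until systolic is ≤159 and diastolic is ≤99, and then say: "After this, lenvatinib may be re-administered". After hospitalization for symptomatic pressure >180 or >110, and after Grade 4, both are stricter: either a permanent stop, or, once pressure is ≤159 and ≤99, possible restart one dose level lower after consulting the principal investigator. The notes to both tables end protocol therapy if managing hypertension delays treatment by more than 2 weeks.

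**D.1 only.** "Decisions to hold or decrease the lenvatinib dose during treatment must be based on BP readings taken in the clinic by a medical professional". D2 has no such sentence.

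**Related text.** Section 7.2 makes control of elevated pressure a condition for continuing and refers failures to Section 8. Section 8.2 sends hypertension management to Appendix IV. Inclusion criterion 3.18 pairs its limits, <150 systolic with <90 diastolic. Section 9.72 and Appendix VI tell patients to contact their physician above 180 systolic or 105 diastolic.

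**The concern.** A rule that can stop drug on diastolic pressure alone should not release it on systolic pressure alone. In footnote 6 it does. It also gives a different systolic limit from the appendix that covers the same decision in more detail.

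Two things are at stake. The first is safety: footnote 6 taken by itself would permit restart while diastolic pressure is still in the range where Appendix IV holds drug (≥100). The second is time on treatment. A patient who settles at 150-159 systolic with diastolic ≤99 may restart under Appendix IV but stays off drug under footnote 6, and the 2-week limit may then end protocol therapy.

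Holds and restarts for hypertension are foreseeable. Section 1.233 reports hypertension in 68% and grade ≥3 in 42% of patients in the cited phase 3 thyroid cancer trial. Section 1.3 gives hypertension as the reason for the reduced 20 mg starting dose.

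**Working it through.** There is no design figure to reproduce. The check sets the rules side by side and applies them to example readings.

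**Rules (S = systolic, D = diastolic, mmHg)**

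- Footnote 6 stop: S >200 or D >110
- Footnote 6 restart: S <150
- Appendix IV restart after a Grade 3 hold, D.1 and D2 alike, outside the hospitalization and Grade 4 cases: S ≤159 and D ≤99

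**Step 1. Footnote 6 against itself.** At 145/112, 112 >110, so drug stops; 145 <150, so the restart condition already holds. The same is true of every reading with D >110 and S <150. A stop triggered by S >200 cannot show this fault, because such a reading fails S <150.

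**Step 2. Footnote 6 against Appendix IV.** Suppose a footnote 6 stop has occurred and a later reading is used to decide on restart. In the first row, the later reading is unchanged.

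| Reading | Footnote 6 restart (S <150) | Appendix IV restart (S ≤159 and D ≤99) |
|---|---|---|
| 145/112 | yes | no (112 >99) |
| 145/105 | yes | no (105 >99) |
| 155/95 | no (155 ≥150) | yes |
| 145/95 | yes | yes |

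In general, S 150-159 with D ≤99 passes Appendix IV only; S <150 with D ≥100 passes footnote 6 only; S <150 with D ≤99 passes both.

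**Step 3. Does any text rank the two?** Sections 7.2, 8.2, 9.5 and 9.72 point towards Section 8 or Appendix IV, but none mentions the footnote 6 limits. The Appendix IV statement giving protocol guidance precedence ranks it over other guidelines such as CTCAE; it does not rank two protocol rules against each other.

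**Step 4. Source of the triggering reading (non-secretory patients only).** Footnote 6 opens with diary readings and then refers to any reading above its limits, so home readings may be meant. That is an inference. If it is right, a home reading of 205/100 calls for an immediate stop under footnote 6, while D.1 requires a clinic reading before a hold. The question would reach the provider, because every footnote 6 value exceeds the contact limits (200 >180 and 110 >105). Home readings are available for Cycles 1-3 at least (Section 9.72, Appendix VI), or throughout therapy under footnote 6. A clinic reading may not be at hand: telephone visits are allowed for non-imaging cycles from Cycle 3, and Section 7.4 lets return visits fall to every 56-60 days.

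**The case against.** The strongest reply is that a provider who follows the whole protocol would not restart at 145/112. Section 7.2 requires elevated pressure to be controlled, Section 8.2 sends the decision to Appendix IV, and Appendix IV holds drug until diastolic is ≤99. The Appendix IV restart is permissive, so waiting for <150 and ≤99 satisfies both rules. Antihypertensives can be stepped up every 24-48 hours, so being stuck at 150-159 for more than 2 weeks may be uncommon. All of this stands, and it lowers the practical risk. It does not supply the missing diastolic limit or say which systolic limit applies.

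The reply on the trigger also has force. Footnote 6 is attached to a row of scheduled visits and does not name the source of the reading. It says a reading should prompt cessation, and the Appendix IV tables are headed as recommendations. D.1's sentence can be taken to cover routine dose changes, since the table separately orders a stop for symptomatic pressure >180 or >110. A reader might infer an outright contradiction over home readings for every patient. The documents do not support that: the home source is inferred, and D2 lacks the clinic-reading sentence.

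A reader might also infer that an extreme reading must persist for 7 days before drug can be held, because the Grade 3 rows are labelled persistent. That definition is worded for dosage reductions, so this goes further than the text.

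**Conclusion.** The restart point holds on the text alone. Footnote 6 gives the wrong result for a diastolic-triggered stop with systolic <150, and its limit disagrees with Appendix IV in two regions: 150-159 with ≤99, and <150 with ≥100. This applies to secretory and non-secretory patients. The trigger point is a lesser ambiguity, confined to non-secretory patients and dependent on footnote 6 covering home readings.

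A reader might conclude that patients will be restarted at 145/112, or forced off therapy by the mismatch. The documents do not show either: other sections steer providers to Appendix IV, and both limits can be met together. They give no frequency for pressure above 200 or 110, so the number of patients affected is unknown; the 68% and 42% figures cannot stand in for it. The primary endpoint's error rates and sample size are unaffected. This is a safety-rule inconsistency worth correcting because the correction is simple.

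**What to change.** 1. Add a diastolic limit to footnote 6 and use one paired restart rule there and in Appendix IV, with a cross-reference. An example is ≤159 and ≤99. The clinical team may prefer a stricter systolic value, such as <150 with ≤99.
2. State that Appendix IV's conditions after hospitalization for symptomatic pressure >180 or >110, and after Grade 4, still apply and are not replaced by the paired rule. Section 8.2 lists Grade 4 hypertension as discontinuation without the restart option, so align that line too.
3. State whether the 2-week limit runs from a footnote 6 stop.
4. In D.1, state that a home reading >200 systolic and/or >110 diastolic triggers an interim hold pending a prompt clinic recheck.

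The cost is amendment wording. Item 4 brings occasional unscheduled rechecks and short holds for transient or inaccurate home readings. A limit of <150 would keep some patients at 150-159 off drug longer and nearer the 2-week limit; ≤159 and ≤99 avoids that.

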Appendix V Drugs with Risk of Torsades De Pointes

The following list contains medications that are generally accepted as having an increased risk of QT prolongation and/or torsades de pointes. **Concomitant administration of lenvatinib and a medication on this list is prohibited.**

Generic Name	Brand Name	Comments
Amiodarone	Cordarone®, Pacerone®	Low risk torsades de pointes
Arsenic trioxide	Trisenox®	Torsades de pointes
Bepridil	Vasocor®	
Chloroquine	Aralen®	
Chlorpromazine	Thorazine®	
Cisapride	Propulsid®	Restricted availability in U.S.
Clarithromycin	Biaxin®	
Disopyramide	Norpace®	Torsades de pointes
Dofetilide	Tikosyn®	Torsades de pointes
Dolasetron	Anzemet®	
Droperidol	Inapsine®	Torsades de pointes
Erythromycin	Erythrocin®, E.E.S. ®	IV > PO
Halofantrine	Halfan®	
Haloperidol	Haldol®	IV > PO, high doses increase QT prolongation and torsades de pointes
Ibutilide	Convert®	Torsades de pointes, female > male, non-Caucasian > Caucasian
Levomethadyl	Orlaam®	
Mesoridazine	Serentil®	
Methadone	Dolophine®, Methadose®	
Pentamidine	Pentam®, Nebupent®	
Pimozide	Orap®	
Procainamide	Pronestyl®, Procan®, Procanbid®	N-acetylprocainamide causes torsade de pointes, not parent compound
Quinidine	Cardioquin®, Quinaglute®	Torsades de pointes
Sotalol	Betapace®	Torsade de pointes female > male
Sparfloxacin	Zagam®	
Thioridazine	Mellaril®	

Note: The above list is not all-inclusive. Consult your local pharmacist for any questions.

Appendix VI Patient Blood Pressure Diary

Today's date _____

Patient Initials _____

Patient Study ID _____

INSTRUCTIONS TO THE PATIENT:

1. Your blood pressure readings have two numbers. The first number is the pressure in your blood vessels during a heartbeat (systolic), and the second number is the pressure in the vessels when the heart rests in between beats (diastolic). These numbers are usually written with a slash in between them (for example, 110/85).
2. Record the date, then record your blood pressure once daily:
3. If you take your blood pressure at other times of the day, please record the numbers and time under "Other readings".
4. Normal blood pressure is usually considered to be 120/80 mmHg. If your systolic pressure is greater than 140 or your diastolic blood pressure is greater than 90 when you measure your blood pressure. Repeat your blood pressure within 1-4 hours. If your blood pressure is still elevated please contact your doctor's office at [REDACTED] for instructions. Also, you should contact your doctor's office at any time your blood pressure exceeds 180 mmHg (systolic) or 105 mmHg (diastolic), or at any time you have symptoms that you think may be related to hi blood pressure (examples include headache, nausea, vomiting, confusion, anxiety, restlessness). If you need to call after business hours or during holidays or weekends, please call [REDACTED] and ask for the Medical Oncologist on call.
5. Please bring this form to your visit at the end of Cycle 1, 2 and 3.

Date	Blood Pressure readings	Other readings (include time of day)	Date	Blood Pressure readings	Other readings (include time of day)
	/			/	
	/			/	
	/			/	
	/			/	
	/			/	
	/			/	
	/			/	

Date	Blood Pressure readings	Other readings (include time of day)	Date	Blood Pressure readings	Other readings (include time of day)
	/			/	
	/			/	
	/			/	
	/			/	
	/			/	
	/			/	
	/			/	
	/			/	
	/			/	
	/			/	
	/			/	
	/			/	
	/			/	
	/			/	
	/			/	
	/			/	
	/			/	
	/			/	
Patient's Signature: _____					
Date: _____					
Physician's Office will complete this section:					
Date of this clinic visit		Physician/Nurse/Coordinator's Signature			

Appendix VII FACT-G (Version 4)

Below is a list of statements that other people with your illness have said are important. **Please circle or mark one number per line to indicate your response as it applies to the past 7 days.**

PHYSICAL WELL-BEING		Not at all	A little bit	Some- what	Quite a bit	Very much
GP1	I have a lack of energy	0	1	2	3	4
GP2	I have nausea	0	1	2	3	4
GP3	Because of my physical condition, I have trouble meeting the needs of my family	0	1	2	3	4
GP4	I have pain	0	1	2	3	4
GP5	I am bothered by side effects of treatment	0	1	2	3	4
GP6	I feel ill	0	1	2	3	4
GP7	I am forced to spend time in bed	0	1	2	3	4
SOCIAL/FAMILY WELL-BEING		Not at all	A little bit	Some- what	Quite a bit	Very much
GS1	I feel close to my friends	0	1	2	3	4
GS2	I get emotional support from my family	0	1	2	3	4
GS3	I get support from my friends	0	1	2	3	4
GS4	My family has accepted my illness	0	1	2	3	4
GS5	I am satisfied with family communication about my illness	0	1	2	3	4
GS6	I feel close to my partner (or the person who is my main support)	0	1	2	3	4
Q1	Regardless of your current level of sexual activity, please answer the following question. If you prefer not to answer it, please mark this box  and go to the next section.					
GS7	I am satisfied with my sex life	0	1	2	3	4

Please circle or mark one number per line to indicate your response as it applies to the past 7 days.

EMOTIONAL WELL-BEING

		Not at all	A little bit	Some- what	Quite a bit	Very much
GE1	I feel sad	0	1	2	3	4
GE2	I am satisfied with how I am coping with my illness	0	1	2	3	4
GE3	I am losing hope in the fight against my illness	0	1	2	3	4
GE4	I feel nervous	0	1	2	3	4
GE5	I worry about dying	0	1	2	3	4
GE6	I worry that my condition will get worse	0	1	2	3	4

FUNCTIONAL WELL-BEING

		Not at all	A little bit	Some- what	Quite a bit	Very much
GF1	I am able to work (include work at home)	0	1	2	3	4
GF2	My work (include work at home) is fulfilling	0	1	2	3	4
GF3	I am able to enjoy life	0	1	2	3	4
GF4	I have accepted my illness	0	1	2	3	4
GF5	I am sleeping well	0	1	2	3	4
GF6	I am enjoying the things I usually do for fun	0	1	2	3	4
GF7	I am content with the quality of my life right now	0	1	2	3	4

